7.2 Concomitant Medications/Treatments

Administration of any concomitant medications, therapies or vaccines will be documented in the subject's data collection form and reported on the subject's data acquisition screen. Concomitant medications will include all current medications and medications taken within the 30 days prior to enrollment (prescription and over-the-

counter drugs, vitamins and supplements, topical products, vaccinations, and allergy shots) through 34 days after the second vaccination (approximately Day 90 for subjects who receive both doses of vaccine or approximately Day 30 for subjects who receive only one dose of vaccine) or early termination (if prior to Day 90), whichever occurs first. Assessment of eligibility also will include a review of permitted and prohibited medications (per the exclusion criteria).

Immunosuppressant medications, as defined by exclusion criterion #22, and medications for the treatment of HCV infection will be collected for the duration of the study.

Medications that might interfere with the evaluation of the investigational product should not be used unless absolutely necessary. Medications in this category include, but are not limited to, glucocorticoids, i.e., oral, parenteral and high-dose inhaled steroids, and immunosuppressive or cytotoxic drugs. Other than from participation in this study, subjects should not receive experimental agents including vaccines during the 20-month study period. The administration of licensed vaccines should be delayed until 14 days after the last study vaccination. Subjects should also not receive licensed products from participation in another clinical trial.

7.3 Prevention: Counseling and Risk Reduction

Prevention counseling for risk avoidance and harm prevention for HCV and other blood borne infections (HIV, HBV) will be provided to all study subjects (in both study arms) at each study visit where HCV testing occurs. Counseling will emphasize the unknown efficacy of the study product in preventing HCV infection (and or other blood borne infections). Subjects will be counseled that stopping injecting will significantly reduce risk of HCV, and that reducing injecting, consistent use of clean needles and drug preparation equipment may also prevent parenteral transmission and acquisition of HCV, if injecting. As well, at each visit study subjects will be provided with free sterile needles and syringes (supplied by local Public Health Departments and/or local syringe exchange programs) and condoms. Members of the Protocol Team will monitor selfreported injection rates, including use of clean and used needles and drug preparation equipment. Risk counseling methods will be updated if needed to address higher than expected rates of reported unsafe behavior and to promote reduction of parenteral risk of HCV by study subjects. In addition to risk reduction information, referral lists of educational resources, community and social service providers, and clinics will be made available. Individuals who are identified as anti-HCV positive at eligibility screening will be referred to established services in each locale. Where possible, medical and social service providers who are experienced in working with the trial population will receive referrals preferentially.

7.4 Contraception Status and Pregnancy

Women of childbearing potential (not surgically sterile via tubal ligation, bilateral oophorectomy or hysterectomy or who have not been postmenopausal for ≥1 year) must agree to practice adequate contraception from the day of the screening visit through 90 days after the second vaccination. Acceptable birth control methods for the purposes of this study may include, but are not limited to: abstinence; monogamous relationship with vasectomized partner; barrier methods such as condoms, diaphragms, spermicides, and intrauterine devices; and licensed hormonal methods.

Contraceptive status is assessed and documented at every scheduled clinic visit for subjects who were born female and who are sexually active in a way that could lead them to becoming pregnant. Prior to enrollment and throughout the study, staff will ask subjects to verbally confirm their use of adequate contraceptive methods. A subject who was born female and is sexually active in a way that could cause that subject to become pregnant should be reminded at all scheduled clinic visits of the importance of using contraception and should be referred to specific counseling, information, and advice as needed. This reminder should be documented in the subject's study record. Self-reported infertility—including having reached menopause (no menses for 1 year) or having undergone hysterectomy, bilateral oophorectomy, or tubal ligation—must be documented in the subject's study record.

Vaccinations will be discontinued for subjects who become pregnant during the course of the study. Pregnant subjects will attend the remaining visits and study procedures should be completed unless medically contraindicated. If the subject terminates from the study prior to the pregnancy outcome, the site must keep in touch with the subject in order to ascertain the pregnancy outcome.

7.5 Behavioral Risk Assessment Questionnaire

A clinic interviewer/clinician will administer a Behavioral Risk Assessment Questionnaire as specified in the study schedule (Section 8). The Behavioral Risk Assessment will query subjects' self-reported HCV risk including injection frequency, use of clean and used needles and drug preparation equipment, drugs used, and behaviors injecting partners. All subjects will receive risk reduction counseling as detailed in Section 7.3.

7.6 Laboratory Evaluations

All laboratory testing will be conducted at CLIA certified laboratories at each site. Blood specimens and volumes will be obtained in accordance with the schedule (Appendix C). Blood specimens that will be collected as part of the standard specimen collection protocol will include serum and anticoagulated plasma. These specimens may be used for (1) repeat analysis of safety and efficacy parameters; (2) analyses of anti-HCV; (3) HCV viral nucleic acids; and (4) antibodies to adenovirus (anti-ChAd3). Blood samples

for isolation and cryopreservation of peripheral blood mononuclear cells (PBMCs) are collected for use in immunology studies. Blood samples collected for immunology analyses at the San Francisco site will be processed for PBMC at Blood Systems Research Institute (BSRI) using a standardized research operating protocol, and shipped to the HCV Immunology Laboratory of [name] at Johns Hopkins University in Baltimore for laboratory analyses of host antiviral immune responses. PBMC for the UNM site will be processed at the UNM Division of Epi/Biostat Molecular Epidemiology Lab and shipped to JHU.

7.6.1 Clinical Laboratory Evaluations

Urine or serum pregnancy tests will be performed within 24 hours prior to each vaccination on all female subjects of childbearing potential. Results must be negative and known prior to vaccination.

Subjects will be tested for HIV antibodies and Hepatitis B surface antigen at screening and the last visit.

Clinical laboratory evaluations for safety will be performed by local (clinical) laboratories. Venous blood samples (approximately 23 mL) will be collected from each subject prior to each vaccination and according to the Study Schedule in Appendix C. Clinical safety lab parameters to be followed include WBC, HgB, platelets, ALT, and creatinine. Urine will be collected to evaluate glucose and protein, which will be performed at screening only.

Human Leukocyte Antigen (HLA) and IL28B typing will be performed for all subjects. IL28B testing and typing will be done at screening/enrollment to inform the randomization process. HLA typing will be done on collected blood samples from vaccinated subjects to inform immunogenicity assessments.

7.6.2 Endpoint Assays: HCV serology and virology

HCV RNA

HCV RNA will be monitored using both qualitative and quantitative assays.

Qualitative HCV RNA testing:

A standardized HCV RNA qualitative assay (Procleix[®] HIV-1/HCV assay, by Gen-Probe Inc., San Diego, CA) with 50% limit of detection of 12.1 copies/mL of HCV RNA when using the recommended 0.5 mL specimen input (95% CI, 11.1 to 13.2) will be used to screen for HCV RNA at monitoring visits. HCV reactive samples will be confirmed using a quantitative HCV RNA assay based on real-time PCR (Procleix HCV assay; Gene-Probe). (This assay will not be used for HIV screening).

Quantitative HCV RNA testing:

Quantitative HCV RNA testing (based on real-time PCR (Procleix HCV assay; Gene-Probe) will be used to confirm HCV infection. Monitoring of HCV infection relies on sensitive and accurate HCV RNA detection by quantitative assays. Recently developed tests based on real time PCR have a high sensitivity (based on the lower limit for detecting HCV RNA) and a great dynamic range. The principle of real-time PCR techniques is to detect amplicon synthesis and to deduce the number of viral genomes in the start of the clinical sample during the PCR rather than at the end. The main advantage of tests based on real time PCR is that each has been standardized, which makes results by different laboratories comparable through reporting in international units (IU).

HCV subtypes

HCV genotype will be determined by reverse transcription/nested PCR (nt 85--1326 core-E1 region amplicon) following nucleic acid extraction on automated instrumentation. Genotype is determined by sequence comparison with GenBank using BLAST. Viral sequencing of HCV Core-E1 sequences of initial infections will be conducted to determine HCV subtype on the first quantitative measurement of HCV RNA, dependent on specimen availability and RNA level. In patients who demonstrate alternating HCV RNA positive and negative results or who have missed more than two follow up study visits, viral sequencing will be used to confirm reinfection with a different virus or intercalating viremia with the same virus.^{29,84}

HCV antibodies

Anti-HCV testing (counseling will be given prior to testing blood for these blood-borne viruses), will be performed at screening and at indicated time points during the study. Anti-HCV antibody testing will be done using a commercial enzyme immunoassay (EIA). Following a positive EIA test in individuals who are not documented to have evidence of an HCV infection (positive HCV RNA), additional testing for HCV antibodies will be done at the end of the study to differentiate infection-induced antibodies from vaccine-induced HCV antibodies (anti-HCV). Differentiation will be based on detection or not of antibodies to antigens not present in the vaccine.

Anti ChAd3 antibodies

Antibodies specific for the ChAd3 virus will be monitored at indicated time points (Appendix C) at Okairos laboratories by using an experimental assay.

7.6.3 Immunogenicity Evaluations

Interferon-gamma (IFN-γ) ELISpot will be used to examine HCV specific T-cell responses following vaccination.

ELISpot Assay

Samples for assessment of vaccine immunogenicity will be collected at the indicated time points (Appendix C). The primary immunogenicity assay is the ex vivo ELISpot assay for IFN-y with peptide pools derived from the HCV genotype1b BK virus used in the vaccine as antigen. IFN-y is a cytokine critical in mediating the adaptive T-cell response to viral infections. It is secreted by activated antigen-specific CD8 T-cells and by the CD4 helper T-cells required to sustain effective CD8 T-cell responses. The ELISpot assay is an efficient, simple, and sensitive method of assessing the total T-cell (sum of CD8+ and CD4+) response to viral antigens. Peripheral blood mononuclear cells (PBMCs) will be isolated from whole blood and frozen according to validated SOPs. PBMC will be thawed according to Okairos SOP IU008 (Human PBMCs triage) and assessed for HCV specific immune responses via a human IFN-y ELISpot assay based on Okairos' standard operating procedure. This Okairos SOP has been already used to measure anti-HCV immune responses in vaccinated volunteers in previous trials: HCV001 (EudraCT number 2007-004259-12), HCV002TV (EudraCT number 2008-006127-32), HCV003 (EudraCT number 2009-018260-10) and HCV004 (EudraCT number 2010-022700-49). Thawed PBMCs will be incubated for 16 hours with HCV antigens in 15-mer peptide pools (overlapping by 11 amino acids) covering the entire NS3-NS5b sequence contained in the vaccine. Peptides 15 amino acid-long have been shown to optimally allow stimulation, and consequently detection, of both CD8+ and CD4+ T-cell responses.⁸⁵ To facilitate the analysis the 494 nonstructural HCV peptides, the peptides are dissolved in DMSO, and divided into 6 mixtures, or pools for screening: pool NS3p (NS3 protease, aa 1027-1349), pool NS3h (NS3 helicase, aa 1339-1661), pool NS4 (NS4, aa 1655-1977), pool NS5a (NS5a, aa 1971-2425), pool NS5bl (NS5b aa 2415-2725) and pool NS5bll (NS5b aa 2715-3011)

Depending on availability of PBMCs, additional assays will be performed on selected samples to further characterize cross-reactivity, function, and phenotype of the induced response as detailed in Sections 7.6.4-5.

7.6.4 Exploratory Assays

Exploratory studies may include measurements of serum or plasma cytokine and chemokine profiles, intracellular cytokine staining to determine if HCV specific T-cells can secrete multiple cytokines in addition to IFN-γ and if they degranulate, or additional T-cell assays for function based on specimen availability.

7.6.5 Ancillary Assays

Ancillary studies may include but are not limited to epitope mapping, tetramer analysis by flow cytometry, and vector-specific immunogenicity. Vector-specific studies may be performed to better understand the immune responses to the vector and vaccine insert. This information may help further product development. Cryopreserved samples may also be used to perform assays to support standardization and validation. Additional cell surface markers, cytokines or functional markers may also be analyzed.

7.6.6 Future use of stored specimens

HCV vaccine researchers aim not only to test vaccine candidates but also to continue to explore the correlates of immunity to HCV. In order to do so, the research team intends to store plasma, serum, and PBMC samples from subjects at UCSF and JHU. These stored samples will be used for future testing and research related to furthering the understanding of HCV or vaccines, such as immunologic analyses in addition to those outlined in sections 7.6.3-7.6.5 and future potential bridging studies.

The protocol ICF is written so that the subject is informed that by agreeing to participate in the study they are also agreeing to have samples stored for future additional research studies. Some of these samples will be sent to a DMID central storage facility. Subjects will not be contacted with the results of these future research studies. Future testing on specimens will only occur to the extent authorized in each study site's ICF or as otherwise authorized under applicable law and after review and approval by the DMID and the IRB of the researcher requesting the specimens.

7.7 Specimen Preparation, Handling, and Shipping

Biological specimens are to be collected in accordance with protocol specifications, as outlined in the Protocol Schedule of Activities. Study staff will follow all safety guidelines of local safety committee and/or institutional policies for handling biological specimens. Blood samples will be labeled and processed according to the protocol-specific MOP. Samples will be barcoded and entered into the GlobalTrace Inventory system before shipping, as indicated in the protocol-specific MOP.

The blood test for detection of anti-HCV, urine test for glucose and protein, and urine pregnancy test will be performed on site. All other specimens will be collected and shipped as indicated in the protocol-specific MOP.

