2.4 Potential Risks and Benefits

2.4.1 Potential Risks

Potential risks

The general risks to subjects in this study are associated with phlebotomy and with vaccination. The volume of blood drawn over the study period, should not compromise health status. Potential risks include local and systemic reactions as vaccine-related side effects, which are described below. Safety data from the ongoing studies described above predicts for mild to moderate reactogenicity of vaccination.

Local reactions

Mild tenderness, bruising, light-headedness or, rarely, syncope, may result from venipuncture. Vaccination usually precipitates a local inflammatory reaction. This may include redness, swelling, tenderness, or itching.

Systemic Reactions

The potential systemic reactions to immunization with vaccines include a flu-like illness with low-grade fever, chills and malaise. As with any vaccine, serious allergic reactions may occur. Monitoring will be ongoing for all of these potential rare events.

Subsequent positivity for hepatitis C antibody (anti-HCV)

It is expected that after vaccination subjects may become anti-HCV positive. In the previous clinical trial, HCV001, anti-HCV positivity in the absence of documented infection occurred in 10% of vaccinated subjects. Anti-HCV seroconversion may occur as a result of exposure to antigens derived from the hepatitis C virus that are included in the vaccine. In order to reassure subjects and maintain coherent health records, subjects will have blood taken for HCV RNA testing [using polymerase chain reaction

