(PCR) methods] prior to the trial to exclude the presence of HCV. No anti-HCV testing will occur systematically during the trial. Only HCV RNA results will be used for determination of HCV infection status during study visits. Anti-HCV testing will be conducted at the end of the trial to examine whether subjects seroconverted (became anti-HCV antibody positive) during the trial. Among subjects who did not have detectable HCV infection, testing will be done to best ascertain whether subjects seroconverted: (1) in association with undetected (HCV RNA) infection, or (2) as a result of vaccination. This testing will be done at the end of the trial, so as not to unblind subjects or investigators during the trial. If the determination is made that subjects became anti-HCV positive as a result of vaccination rather than infection, they will be provided with documentation explaining the reasons for their anti-HCV positivity. These cards will have contact information for study investigators so that providers can communicate as necessary regarding subject's anti-HCV status (with the subject's consent). This will be discussed in detail with subjects at screening and in informed consent forms (ICFs).

Confidentiality

The risk of study participation includes possible loss of confidentiality. Risks to privacy and confidentiality exist with all human research. Subjects will be assigned a unique study identification number which will be used on data collection forms, case report forms (CRFs), and specimens collected for laboratory analyses. No samples or data will be labeled with the subject's name. The key to subjects' names will be accessible only to the study co-principal investigators, and hard-copies and electronic copies of data will be stored in secured locations.

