8.2.14 Days 390–570, Visits 19–25

Visit	Target (Day)	Window (Days)
19	390	+ 7
20	420	+ 7
21	450	+ 7
22	480	+ 7
23	510	+ 7
24	540	+ 7
25	570	+ 7

- Current health status will be reviewed and any changes since the last visit will be noted.
- A targeted physical examination may be performed, if indicated, based on review of current health status.
- Behavioral risk will be assessed using an interviewer administered questionnaire at visits 21 and 24.
- Immunosuppressant concomitant medications and medications for the treatment of HCV infection will be recorded.
- SAEs that have occurred since the last contact will be collected.
- Approximately 10 mL of venous blood will be collected for HCV viremia.
- Counseling on avoidance of HCV and HIV infection, and pregnancy will be conducted.
- Referral to drug treatment and needle exchange programs will be provided.

8.2.15 Day 600, Visit 26

(Window: Day 593 to 607)

- Current health status will be reviewed and any changes since the last visit will be noted.
- A targeted physical examination may be performed, if indicated, based on review of current health status.
- Behavioral risk will be assessed using an interviewer administered questionnaire.
- Immunosuppressant concomitant medications and medications for the treatment of HCV infection will be recorded.
- SAEs that have occurred since the last contact will be collected.
- Approximately 23 mL of venous blood will be collected for hematology and biochemistry parameters, as described in Section 7.6.1, and performed by the

local laboratory.

- Approximately 20 mL of venous blood will be collected for anti-HCV, HbsAg, anti-HIV and HCV viremia.
- Approximately 100 mL of venous blood will be collected for immunologic assays.
- Counseling on avoidance of HCV and HIV infection, and pregnancy will be conducted.
- Referral to drug treatment and needle exchange programs will be provided.
- Subjects will be thanked for participating in the study and contact information for end of study results will be confirmed.

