8.5.1 For HCV-uninfected subjects

- Current health status will be reviewed and any changes since the last visit will be noted.
- All concomitant medications will be recorded (if prior to Day 90 visit). Immunosuppressant medications and medications for the treatment of HCV infection will be collected throughout the study as applicable.
- Approximately 23 mL of venous blood will be collected for hematology and biochemistry parameters, as described in Section 7.6.1.
- Approximately 100 mL of venous blood will be collected for immunologic assays.
- Approximately 20 mL of venous blood will be collected for anti-HCV, HbsAg, anti-HIV, and HCV viremia.
- A targeted physical examination may be performed, if indicated based on review of current health status.
- Information regarding adverse events will be collected (if before Day 90). All SAEs that have occurred since the last contact will be collected.
- Subjects will be thanked for participating in the study and contact information for end of study results will be confirmed.

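### Anti-HCV testing is deferred to protect the blind, but other sections allow it on site during the study, and nothing holds or masks the last-visit and early-termination samples

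*Protocol*

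**What the plan says.** Protocol 2.4.1 expects some vaccinees to become anti-HCV positive and sets a rule to protect the blind: "No anti-HCV testing will occur systematically during the trial". Of the tests that separate vaccine-induced from infection-induced antibody it says: "This testing will be done at the end of the trial, so as not to unblind subjects or investigators during the trial". Section 5.3 keeps subjects blinded until the trial closes.

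Other sections read differently:

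- Section 7.6.2 says anti-HCV testing "will be performed at screening and at indicated time points during the study". Only the additional differentiating test is assigned there to the end of the study.
- Section 7.7 says "The blood test for detection of anti-HCV, urine test for glucose and protein, and urine pregnancy test will be performed on site"; all other specimens are collected and shipped. Section 7.6 places laboratory testing at certified laboratories at each site.
- Section 8.2.15 (Day 600, Visit 26) says "Approximately 20 mL of venous blood will be collected for anti-HCV, HbsAg, anti-HIV and HCV viremia". Section 8.5.1 (early termination, uninfected subjects) says "Approximately 20 mL of venous blood will be collected for anti-HCV, HbsAg, anti-HIV, and HCV viremia". Appendix C gives anti-HCV its own 5 mL line at both visits.

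The size of the serological effect is given in 2.4.1 for HCV001: "anti-HCV positivity in the absence of documented infection occurred in 10% of vaccinated subjects".

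**The concern.** A site that follows 7.6.2, 7.7 and Appendix C as written could run the antibody test when a subject finishes or withdraws, years before the trial closes. The same visit includes an HCV RNA test. A subject who is RNA negative and antibody positive then looks like a vaccinee to the site investigator.

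Those investigators still have blinded judgements to make. SAP 6.3.3 gives ATP membership to a blinded team that includes the site PIs. Some of its criteria need judgement: whether an eligibility failure could affect efficacy, and whether immune deficiency is suspected. ATP is the primary efficacy population. Site investigators also judge whether an SAE is related to vaccine (Protocol 9.4), which defines a primary safety endpoint (3.1.1). SAEs can still arrive after the antibody result, through the 6-month call after early withdrawal (8.5) or after completion (9.3.1). SAP section 11 records more early discontinuation than anticipated, so the early-termination route is not rare.

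**Working it through.** **Do the sections agree?** Section 2.4.1 excludes systematic testing during the trial, while 7.6.2 provides for it at set time points. Section 7.7 puts the test on site without qualification. The schedule supplies a tube at two post-vaccination visits. No section says the tube is held until close or the result withheld from site staff. Equally, no section says the tube is assayed at that visit; the schedule lists volumes collected. So the text permits on-site testing at these visits but does not direct it.

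**How long before close?** Planned duration (Protocol section 4): 31 months of accrual + 3 halted + 2 vaccination + 18 follow-up + 9 extended = 63 months, which reproduces the stated figure. Enrolment ends at 31 + 3 = month 34. Visit 26 falls about 20 months after enrolment.

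- First subject enrolled, Visit 26: 63 − 20 = 43 months before close, and 34 − 20 = 14 months before enrolment ends.
- Last subject enrolled, Visit 26: 63 − (34 + 20) = 9 months before close.
- First subject enrolled, early termination (30.44 days per month): at Day 56, 63 − 56/30.44 = about 61 months; at Day 90, 63 − 90/30.44 = about 60 months.

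These gaps use the full 63 months. If no late infection extended follow-up, close would come at 34 + 20 = month 54, and the Visit 26 gaps would run from 34 months down to 0.

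**How many subjects?** At the HCV001 rate, 0.10 × 270 = 27 vaccinees, or 27/540 = 5% of all subjects. At that rate 27 is a ceiling, because it assumes that every vaccinee stays uninfected and gives a final sample. For scale, the 65% ATP retention assumed in 11.2 would give 0.65 × 27 = about 18. The rate itself is imprecise. HCV001 had 41 subjects (2.2.3). If 10% means 4 of 41, an assumption, the exact 95% interval is about 3% to 23%, or roughly 7 to 62 of 270.

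**How much would a result tell the investigator?** With 1:1 allocation, let q be the placebo rate of RNA-negative, anti-HCV-positive results. The documents give no value for q, so a range is assumed. P(vaccine | positive) = 0.10/(0.10 + q):

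- q = 0%: 100%
- q = 1%: 0.10/0.11 = 91%
- q = 3%: 0.10/0.13 = 77%
- q = 5%: 0.10/0.15 = 67%

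A negative result is almost uninformative: P(vaccine | negative) = 0.90/(0.90 + 1 − q), which is 47% at q = 0 and 49% at q = 5%.

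**The case against.** The best counter-case is that the protocol already intends late testing and only the wording is loose.

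- The sentence in 7.7 may describe screening. It groups anti-HCV with urine glucose and protein, which 7.6.1 limits to screening, and it resembles the description of the pre-screening test in 8.1.1.
- Section 7.6.1 names only HIV antibody and HBsAg as tested at screening and the last visit.
- Section 8.7 refers to stored samples and to informing subjects with vaccine-induced antibody at study end.
- The Manual of Procedures, which is not available here, may tell sites to hold the tube.

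This stands as far as it goes, and it is why testing at the visit cannot be asserted as fact. It does not remove the conflict. The same sentence in 7.7 covers the urine pregnancy test, which is repeated before dose 2 (8.2.5), so it is not confined to screening. Where the protocol means screening only, as for urine glucose and protein, it says so. The stored-sample sentence in 8.7 follows the step that begins with a positive EIA, and it gives no hold date for that first EIA.

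A second objection is that little bias can follow. Most ATP criteria are factual, and a completer's scheduled RNA and SAE collection is ending at Visit 26. That is fair, and it limits the consequence. It does not cover the judgement-based ATP criteria or SAEs reported later.

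A reader might infer something stronger: that the schedule orders an on-site test at every last visit, and that this reveals the arm of about 27 vaccinees up to 43 months before close. The documents do not support that. Testing at the visit is nowhere stated. Section 2.4.1 gives two causes of such a positive, "in association with undetected (HCV RNA) infection, or (2) as a result of vaccination", and further antibody tests are needed to separate them. The 43 months belongs only to the first enrollee's Visit 26.

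**Conclusion.** The protocol contradicts itself on when and where anti-HCV is tested, and it has no hold or masking rule for the Visit 26 and early-termination samples. The conflict undercuts a safeguard that the protocol itself considered necessary.

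If sites test at the visit, the result is partial unblinding: a strong hint for at most about 27 vaccinees at the 10% rate, and almost nothing for everyone else. This rests on three assumptions: that sites act on 7.6.2 and 7.7 as written, that the HCV001 rate (adenoviral vectors without the MVA boost) carries over, and that few placebo subjects are antibody positive without detected RNA.

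The exposure is mainly in site-PI judgements on ATP membership and SAE relatedness. No route to the RNA-based endpoint data is shown. The point should be corrected, but it does not in itself undermine the primary efficacy result.

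**What to change.** - In 7.7, limit the on-site anti-HCV test to pre-screening and screening.
- In 7.6.2, 7.7, 8.2.15, 8.5.1 and Appendix C, state that Visit 26 and early-termination anti-HCV samples from HCV-uninfected subjects are stored. State that the EIA and differentiating tests are run in one batch, only after the last subject's last visit and after ATP membership and case adjudication are locked. This brings those sections into line with 2.4.1.
- Leave H09 unchanged for blinding purposes. Those subjects are already known to be infected, so a positive antibody result does not point to vaccine.

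The cost is protocol and Manual of Procedures wording, plus storage of a tube that is already drawn. The batch must be finished before the final analysis, because the SAP's secondary definition of incident infection (3.3.3) uses these results; SAP 6.2 already waits for all research laboratory data. The downside is that subjects receive the antibody result at study end. HCV RNA is still tested at the same visit.
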